### **7.1.3      Allowed Medications**

All treatments that the Investigator considers necessary for a patient's welfare may be administered at the discretion of the Investigator in keeping with the community standards of medical care. All concomitant medication will be recorded on the eCRF including all prescription, over-the-counter (OTC), herbal supplements, and IV medications and fluids. If changes occur during the study period, documentation of drug dosage, frequency, route, and date may also be included on the eCRF.

All concomitant medications received within 28 days before the first dose of investigational product and 30 days after the last dose of investigational product should be recorded.

Confidential

Document State: Effective (Controlled)  
CONFIDENTIAL

Page 65 of 118

Concomitant medications administered after 30 days after the last dose of investigational product should be recorded for SAEs and AESIs as defined in Section 8.4. In addition, all prior therapies for ACC should be recorded.

Allowed concomitant therapies:

- Glucocorticoids may be administered for treatment of infusion reaction and as premedication to prevent further infusion reaction (maximum daily dose of prednisone or equivalent  $\leq$  10 mg/day).
- In Cohort 2, in case of toxicity (e.g., GI AEs), per discretion of the Investigator and in consultation with the Sponsor's Medical Monitor, dexamethasone (Refer to Section 7.1.2) will be permitted.
- Palliative radiation therapy to a limited field (e.g., painful bone metastasis, painful lumps), *if it is not the sole site of measurable and/or assessable disease*, is allowed any time during study participation with prior approval of the Sponsor's medical monitor.
- Patients with castration resistant prostate cancer who have not undergone surgical orchiectomy can continue on medical therapies (i.e., gonadotropin releasing hormone [GnRH] analogs) to maintain castrate levels of serum testosterone. Concurrent treatment with ketoconazole or anti-androgens is not permitted, and patients who have discontinued these medications must have a washout period of at least 4 weeks or 5 half-lives of the drug (whichever is longer) prior to the first dose of investigational product.

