### **9.6 EFFICACY**

#### **9.6.1 Definition of Efficacy Endpoints**

The primary efficacy endpoint is the objective response rate (ORR). ORR is defined as the proportion of patients who have a best overall response (BOR) of CR or PR as determined using RECIST v1.1 or modified MDA criteria for bone-exclusive disease (see [Table 11](#)). BOR is defined as the best response recorded between the date of first dose of investigational product and the date of subsequent anti-cancer therapy. A BOR of CR or PR requires confirmation of the assessment at least 4 weeks later.

Other efficacy endpoints are as follows:

Confidential

Document State: Effective (Controlled)  
CONFIDENTIAL

Page 83 of 118

- DOR, defined as the interval from the first documentation of CR or PR to the earlier of the first documentation of disease progression (per RECIST v1.1) or death from any cause.
- PFS, defined as the interval from the start of investigational product to the earlier of the first documentation of disease progression or death from any cause
- OS, defined as the time from the date of start of treatment to the date of death from any cause. Patients who are lost to follow-up and those not known to have died by the cut-off date for analysis will be censored on the date the patient was last known alive, or the data cut-off date, whichever is earlier.

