#### **Target Lesions:**

- Identify a maximum of 5 **target lesions** (up to 2 target lesions per organ).
  - Target lesions must be **measurable**; where measurable is defined:
    - 10 mm in the longest diameter by CT (preferred) or MRI scan (or no less than double the slice thickness) for non-nodal lesions and  $\geq 15$  mm in short axis for nodal lesions
    - 10 mm caliper measurement by clinical exam
    - 20 mm by chest X-ray
- **NOTE:** Regardless of the imaging modality blastic bone lesions will not be selected as target lesions. Lytic or mixed lytic-blastic lesions with a measurable soft tissue component  $\geq 10$  mm can be selected as target lesions.
- **NOTE:** Lesions having undergone prior intervention (e.g., previous irradiation) will not be selected as target lesions unless there has been a demonstration of progress in the lesion.
- Target lesions should be selected on the basis of their size (lesions with the longest diameter), be representative of all involved organs, but in addition should be those that lend themselves to reproducible repeated measurements.
- Calculate the **sum of the diameters (SOD)** of all target lesions.
  - For non-nodal lesions: the longest diameter should be included in the sum of diameters
  - For nodal lesions: the short axis measurement (i.e., widest dimension perpendicular to the long axis) should be included in the sum of diameters

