6 INVESTIGATIONAL PLAN

6.1 Overall Study Design

This is a Phase 2, non-comparative, open-label, multicenter study of AL101 in patients with recurrent or metastatic ACC who harbor NOTCH 1,2,3,4 activating mutations.

The study includes 2 cohorts, ran in a sequential fashion:

- Cohort 1 – AL101 4 mg once weekly (QW) intravenously (IV)
- Cohort 2 – AL101 6 mg QW IV

Cohort 1 will continue to enroll to reach up to a maximum of 45 patients. Cohort 2 will open for enrollment up to a maximum of 42 patients. Prior to entering the study, to determine eligibility, potential candidates will undergo pre-screening assessment and confirmation for the presence of activating Notch mutations. Available mutation status from prior tests with any commercially available or locally developed NGS assay are acceptable. In Europe any commercially available CE marked device shall be used.

If historical genotyping results are not available, testing will need to be conducted during prescreening using a laboratory developed or commercially available NGS assay to identify and confirm an activating Notch mutation. Any newly characterized mutation (such as tandem duplication, variant allele frequency, variants of unknown significance, etc.), will be evaluated with the Sponsor on a case-by-case basis. Pre-screening studyspecific assessments may be done while potential candidates are on other therapy provided that a separate pre-screening informed consent form is signed.

Patients with activating Notch mutations will then undergo screening assessments to determine study eligibility over a 28-day Screening period. Enrollment of patients with bone exclusive disease should be discussed and approved by the Sponsor's Medical Monitor before enrollment. For all patients, prior treatments and responses to such treatments, including radiological images and reports, within a year of study entry will be collected as part of the medical history; for patients who are currently enrolled, this information will be collected retrospectively.

Starting on Cycle 1, Day 1, eligible patients will receive AL101, either 4 mg QW IV in Cohort 1 or 6 mg QW IV in Cohort 2, on Days 1, 8, 15, and 22 of each 28-day cycle until disease progression, unacceptable toxicity, or consent withdrawal. For patients with radiological progression, investigational product may be continued as long as the patient is having clinical benefit, is agreed to by the patient and physician and approved by the Sponsor's Medical Monitor.

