6.3 Treatment

6.3.1 *Treatment Administered*

AL101 will be administered IV at the dose of 4 mg every 7 days (± 2 day; QW) in Cohort 1 and at the dose of 6 mg every 7 days (± 2 day; QW) in Cohort 2 over 28-day cycles until disease progression, unacceptable toxicity, or consent withdrawal. For patients with radiological progression, investigational product can be continued as long as the patient is having clinical benefit, is agreed to by the patient and physician and approved by the Sponsor's Medical Monitor.

AL101 will be administered using an IV infusion pump over 60 minutes; time windows of -5 minutes to +10 minutes are permitted.

AL101 injection has been developed as a single-use sterile solution (1.2 mg/mL) for IV administration in clinical studies; each vial contains 5 mL (equivalent of 6 mg per vial). It is formulated as a sterile concentrate containing Cremophor® and ethanol and will be diluted with 0.9% Sodium Chloride Injection, USP (normal saline) or 5% Dextrose Injection, USP (D5W) to concentrations between 0.01 mg/mL and 0.06 mg/mL. In order to reduce the risk of infusion reactions caused by Cremophor, use premedication per institution guidelines such as H1- and H2-blockers (diphenhydramine and ranitidine or equivalents) or dexamethasone will be given.

If an infusion is extended, interrupted or discontinued prior to completion, the duration and the reason for any dose extension, interruption or discontinuation will be recorded in the electronic case report form (eCRF).

6.3.2 *Method of Assigning Subjects to Treatment Groups*

This is an open-label design, with all patients assigned sequentially to 1 of 2 cohorts and receive AL101 monotherapy. Cohort 1 enrolled up to a maximum of 45 patients and cohort 2 enrolled up to a maximum of 42 patients.

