6.4 Efficacy and Safety Variables

6.4.1 *Description of Efficacy Variables*

6.4.1.1 *Primary Efficacy Variables*

The primary efficacy endpoint is the objective response rate (ORR).

ORR is defined as the proportion of subjects who have a best overall response (BOR) of complete response (CR) or partial response (PR) as determined by Investigator review

using RECIST v1.1 (Protocol Appendix C) or modified MDA bone criteria for subjects with bone-exclusive disease (Protocol Appendix C, Table 11).

BOR is defined as the best response recorded between the date of first infusion of investigational product and the date of subsequent anti-cancer therapy. A BOR of CR or PR requires confirmation of the assessment at least 4 weeks later. A BOR of SD requires the assessment to be recorded no less than 4 weeks after the start of study medication.

RECIST 1.1 (Eisenhauer 2009) will be used to determine response at each post-baseline time point. Assessment of target lesions, non-target lesions, new lesions, and overall response will be assigned as described in Table 3, Table 4 and Table 5. Table 6 describes the derivation of best overall response from overall response assessments at each visit.

Table 3 RECIST 1.1 Evaluation of Target Lesions:

Response	Definition
CR	Disappearance of all target lesions. Any pathological lymph nodes must have reduction in short axis to < 10 mm.
PR	At least a 30% decrease in the sum of the diameters of target lesions, taking as reference the baseline sum diameters.
PD	At least a 20% increase in the sum of the diameters, taking as reference the smallest sum on study (this includes the baseline sum if that is the smallest on study). In addition to the relative increase of 20%, the sum must also demonstrate an absolute increase of at least 5 mm. The appearance of one or more new lesions is also considered progression.
SD	Neither sufficient shrinkage to qualify for PR nor sufficient increase to qualify for PD, taking as reference the smallest sum diameters on study.

Table 4 RECIST 1.1 Evaluation of Non-target Lesions:

Response	Definition
CR	Disappearance of all non-target lesions and normalization of tumor marker level. All lymph nodes must be non-pathological in size (< 10 mm short axis).
SD	Persistence of one or more non-target lesion(s) or/and maintenance of tumor marker level above the normal limits.
PD	Appearance of one or more new lesions and/or unequivocal progression of existing non-target lesions.

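### The best overall response window does not close at first documented progression, so a response that follows progression can count towards ORR

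*SAP*

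**What the plan says.** **Response window.** SAP 6.4.1.1: "BOR is defined as the best response recorded between the date of first infusion of investigational product and the date of subsequent anti-cancer therapy". Protocol 9.6.1 is worded the same way, counting from first dose. Progression is not named as an end of the window in either place. On confirmation, the SAP adds: "A BOR of CR or PR requires confirmation of the assessment at least 4 weeks later".

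**Treatment after progression.** SAP 6.1: "For patients with radiological progression, investigational product may be continued as long as the patient is having clinical benefit", subject to agreement of patient and physician and to Medical Monitor approval. SAP 6.3.1 and Protocol Section 3 say the same.

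**Other endpoints.** SAP 6.4.1.2 ends both DOR and PFS at the first documented progression or death.

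**Radiation.** Protocol 7.1.3 lists limited-field palliative radiation among the allowed concomitant therapies. If the field is not the only measurable or assessable disease, it "is allowed any time during study participation with prior approval of the Sponsor's medical monitor". Appendix C deals with irradiated lesions only when target lesions are chosen: "Lesions having undergone prior intervention (e.g., previous irradiation) will not be selected as target lesions", unless the lesion has since progressed.

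**The concern.** Partial response is judged against the baseline sum and progression against the smallest sum on study (SAP Table 3). One patient can therefore meet progression first and partial response later. Where treatment may continue past progression, the end of the BOR window decides whether that later response counts. Here it does count, because only a new anti-cancer therapy closes the window.

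Two things are at stake. The primary endpoint can include responses that came after the drug had already failed by the trial's own criterion. ORR, PFS and DOR can also contradict each other within one patient, with no rule for resolving it; the programmer would have to choose after seeing the data. DCR is built on the same BOR and inherits the problem. So do the PFS and OS analyses restricted to patients with a BOR of PR (SAP 7.5.3.2 and 7.5.3.3).

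**Working it through.** **1. Does the written rule count such a patient?** The sums are illustrative; the thresholds are from SAP Table 3 (PR: at least 30% below baseline; PD: at least 20% and 5 mm above the smallest sum).

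| Scan | Sum, mm | Against baseline | Against smallest prior sum | Timepoint response |
|---|---|---|---|---|
| Baseline | 100 | – | – | – |
| 1 | 75 | −25% | −25% | SD |
| 2 | 90 | −10% | (90 − 75)/75 = +20%, +15 mm | PD |
| 3 | 70 | −30% | (70 − 75)/75 = −6.7% | PR |
| 4, at least 4 weeks after scan 3 | 70 | −30% | 0% | PR |

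With no new anti-cancer therapy, BOR as written is PR. With the window closed at scan 2 it is SD, since an 8-week first scan exceeds the 4-week minimum for SD.

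**2. Does another rule stop it?** SAP Table 5 assigns each timepoint on its own. Table 6 has first-timepoint rows for CR, PR and NE only, so PD followed by PR is not addressed, while PR followed by PR gives PR. The sensitivity analyses in SAP 6.4.1.1 and 7.5.2 vary confirmation, reader and analysis set. None ends BOR at progression.

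**3. The same patient in PFS and DOR.** PFS has an event at scan 2. The DOR formula is (date of progression − date of initial response + 1)/30.4375. If scan 3 falls one 8-week interval after scan 2, this gives (−56 + 1)/30.4375 = −1.8 months.

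**4. Size.** The plan's own figure first. For Cohort 2 (SAP 7.9: 21 then 42 patients, r1 = 2, r2 = 6), power is the sum over x = 3 to 21 of P(X1 = x) × P(X2 ≥ 7 − x). At 25% this gives 88.6%, against 89.4% stated; at 8% the type I error is 3.95%. SAP 7.9 says the Cohort 2 futility look was not conducted, which leaves P(X ≥ 7 of 42): 4.75% at 8% and 92.9% at 25%. The BOR window enters none of these formulas, so the stated design is not in dispute.

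Effect of one patient, if every planned patient is evaluable:

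- ORR: 1/42 = 2.4 points in Cohort 2; 1/45 = 2.2 points in Cohort 1.
- Exact one-sided p against 8%: 0.116 for 6/42 and 0.047 for 7/42.
- Clopper-Pearson 95% lower limit: 7.0% for 7/42 and 8.6% for 8/42; 6.5% for 7/45 and 8.0% for 8/45.

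The documents do not say how many patients would be affected. As an assumption, let q be the share of patients who count only through this route, with a true rate of 8%:

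| q | P(X ≥ 7 of 42) at 8% + q | P(X ≥ 8 of 45) at 8% + q |
|---|---|---|
| 0 | 4.7% | 2.5% |
| 1 point | 7.9% | 4.6% |
| 2 points | 12.1% | 7.6% |
| 3 points | 17.4% | 11.6% |

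**5. Radiation.** Protocol 7.1.3 treats limited-field palliative radiation as an allowed concomitant therapy, which suggests that it does not close the window. SAP 7.4.4 puts radiation under prior cancer treatments, and SAP 6.4.2.2 lists it among interventions for the patient's cancer, which suggests that it does. No section settles this or says how a target lesion irradiated on study is assessed.

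**The case against.** The best defence is that the route is narrow. The imaging schedules (Protocol Table 1 note m and Table 2) run on-treatment scans until progression. Long-term follow-up imaging is only for patients who stopped for toxicity, and also ends at progression. The end-of-study visit supplies one scan, but a confirmed response needs two. Under SAP Table 5 a new lesion keeps the overall response at PD while it is recorded, so the gap mainly concerns target-lesion growth, or non-target progression that later reverses. All of this stands, and it limits the number of patients. It does not close the window: the design text in Protocol Section 3 and SAP 6.1 gives the 8-week interval without the progression limit, and the unconfirmed analyses need only one scan.

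A second defence is that response follows RECIST v1.1, that Appendix C defers to the published criteria, and that an Imaging Manual exists. Footnote a of SAP Table 6 also treats disease that reappears after a true CR as PD, which suggests a strict intent. However, SAP 6.4.1.1 invokes RECIST for the response at each timepoint and sets the BOR window in its own sentence, and SAP Section 4 gives the SAP precedence over the protocol. The footnote covers relapse after CR, not response after PD. The manual and the published criteria were not available for this review.

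Third, DOR can be read as running to the first progression after response, so a negative duration is not compelled. That is fair, but the SAP does not say so, and the conflict between ORR and PFS remains. The planned side-by-side listings of local and central responses (SAP 7.5.2) would make such patients visible without removing them from ORR.

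**Conclusion.** The definition should be corrected. As written, a confirmed response after first progression counts in the primary endpoint, while PFS and DOR stop at that progression. Dropping assessments after progression can only remove responders, so the error is one-directional: it can raise ORR and cannot lower it. The likely size is small, at 2.4 points per patient if all 42 in Cohort 2 are evaluable.

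Two stronger readings are tempting, and the documents do not support them.

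- **That radiation-driven shrinkage counts as drug response.** Radiation is restricted to a limited field with prior approval. No section says that an irradiated target lesion stays in the sum, or that such radiation leaves the window open. This is an unanswered question, not a demonstrated bias.
- **That the trial's false-positive rate is inflated to the levels tabulated above.** Those figures rest on an assumed 1 to 3 points. SAP 7.5.2 plans an estimate with a confidence interval and specifies no test; the protocol synopsis speaks of tests only if any are performed. The movement from 6/42 to 7/42 shows how sensitive a boundary result is to one patient. It does not forecast the result.

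The permission to treat beyond progression is not questioned here; only the counting rule is.

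**What to change.** **Main change (SAP 6.4.1.1).** Define the BOR window as running from first infusion to the earliest of first documented PD, by RECIST v1.1 or modified MDA criteria, and the start of subsequent anti-cancer therapy. Make the same change in Protocol 9.6.1 and record it in SAP 7.10. Show any response first recorded after progression in a listing only.

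**Clarification on radiation.** State whether on-study palliative radiation is subsequent anti-cancer therapy. For BOR, state that a CR or PR first recorded after radiation to a target lesion does not count, that later progression still counts as PD, and that a response first recorded before radiation is kept under the usual confirmation rules. Setting target-lesion response to not evaluable from the date of irradiation is a simpler rule, but I would avoid it. It could hide later target-lesion progression from PFS, and under SAP Table 6 it would turn a genuine PR irradiated before confirmation into SD or NE.

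**Cost.** A few sentences in the SAP and an aligned protocol definition; Protocol 9.1 asks for major modifications to be reflected in an amendment. ORR may be slightly lower. Sample size, cut-offs, stated power and treatment rules do not change.

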6.4.1.2 Secondary Efficacy Variables

Secondary efficacy endpoints include the following:

Duration of Response (DOR): defined as the time interval from the initial confirmed response of CR or PR to the earlier of the first documentation of disease progression (per RECIST v1.1 or modified MDA criteria) or death from any cause, as determined by Investigator review. DOR will be calculated in months as (date of disease progression or death/censoring – date of initial response + 1) / 30.4375.

For DOR (and PFS) the date of progression or death and censoring will be based on the Food and Drug Administration (FDA) guidance *Clinical Trial Endpoints for the Approval of Cancer Drugs and Biologics* (May 2007), as defined in Table 7.

Table 7 Determining Date of Progression or Censoring for PFS and DOR Analysis

Situation	Date of Progression or Censoring	Outcome
Alive and without documentation of disease progression.	Date of last disease assessment. All patients still alive and without documentation of disease will be censored as of July 31, 2022.	Censored
Treatment discontinuation for undocumented progression	Date of last disease assessment	Censored
Treatment discontinuation for toxicity or other reason	Date of last disease assessment	Censored
Other anticancer treatment started before documentation of disease progression or death	Date of last disease assessment prior to start of other anticancer treatment	Censored

Death before first disease assessment	Date of death	Progressed
Death or disease progression between planned disease assessments	Date of death or first disease assessment showing disease progression, whichever occurs first	Progressed
Death or progression after more than one missed disease assessment	Date of last disease assessment visit without documentation of disease progression that is before the first missed visit	Censored

As part of the sensitivity analysis, DOR will also be derived as follows:

- As above but where confirmation of PR/CR is not required.
- As above but based on central review rather than Investigator review.
- As above but based on central review rather than Investigator review and where confirmation of PR/CR is not required.

Progression-Free Survival (PFS): defined as the interval from the start of investigational product to the earlier of the first documentation of disease progression (per RECIST v1.1 or modified MDA criteria) or death from any cause, as determined by Investigator review. Progression-free survival will be defined in months as: (date of progression or death/censoring – date of first infusion + 1) / 30.4375.

Patients without disease progression or death will be censored as per Table 7.

As part of the sensitivity analysis, PFS will also be derived as follows:

- As above but based on central review rather than Investigator review.

Overall Survival (OS): defined as the time from the date of start of treatment to the date of death from any cause. Subjects with no documentation of death will be censored at the last date known to be alive, per the data collection. Sites will be asked to search public registries for any possible death dates for subjects who withdrew consent from the study (as per FDA Guidance for Sponsors, Clinical Investigators, and IRBs

Data Retention When Subjects Withdraw from FDA-Regulated Clinical Trials). Where it is possible for this search to be done, any deaths found will be included in the analysis. Overall survival time will be calculated in months as (date of death/censoring – date of first infusion + 1) / 30.4375.

As part of the sensitivity analysis, OS will also be derived as follows:

- As above but where date of first diagnosis of recurrent or metastatic disease is used instead of date of first infusion.
- As above but where date of initial ACC diagnosis is used instead of date of first infusion.

Time to Response (TTR): defined as the interval from the start of investigational product to the initial (subsequently confirmed) response of CR or PR (per RECIST v1.1 or modified MDA criteria), as determined by Investigator review. TTR will be calculated in months as $(\text{date of initial response/censoring} - \text{date of first infusion} + 1) / 30.4375$.

Patients without response will be right censored at their last tumor assessment.

As part of the sensitivity analysis, TTR will also be derived as follows:

- As above but where confirmation of PR/CR is not required.
- As above but based on central review rather than Investigator review.
- As above but based on central review rather than Investigator review and where confirmation of PR/CR is not required.

Disease control rate (DCR): defined as the proportion of subjects who have a BOR of CR, PR or SD as determined by Investigator review using RECIST v1.1 (per RECIST v1.1 or modified MDA criteria). A BOR of CR or PR requires confirmation of the assessment at least 4 weeks later. A BOR of SD requires the assessment to be recorded no less than 4 weeks after the start of study medication.

As part of the sensitivity analysis, DCR will also be derived as follows:

- As above but where confirmation of PR/CR is not required.
- As above but based on central review rather than Investigator review.
- As above but based on central review rather than Investigator review and where confirmation of PR/CR is not required.

European Organization for Research and Treatment of Cancer Quality of Life Questionnaire (EORTC QLQ-C30): quality of life, as measured by EORTC QLQ-C30, will be assessed during the study every 4 weeks, prior to investigational product administration. The QLQ-C30 questionnaire is composed of 5 multi-item scales (physical, role, social, emotional and cognitive functioning) and 9 single items (pain, fatigue, financial impact, appetite loss, nausea/vomiting, diarrhea, constipation, sleep

disturbance and quality of life) (Kyriaki, 2001). It is validated and reliable and has been used successfully in various types of cancer, including head and neck cancer.

Individual items contribute to the scales as shown below:

Table 8 EORTC QLQ-C30 Scales

	Scale	Number of Items	Item Range*	Item Numbers
Global health status / QoL				
Global health status / QoL (revised) [†]	QL2	2	6	29, 30
Functional scales				
Physical functioning (revised) [†]	PF2	5	3	1 to 5
Role functioning (revised) [†]	RF2	2	3	6, 7
Emotional functioning	EF	4	3	21 to 24
Cognitive functioning	CF	2	3	20, 25
Social functioning	SF	2	3	26, 27
Symptom scales / items				
Fatigue		FA	3	10, 12, 18
Nausea and vomiting	NV	2	3	14, 15
Pain	PA	2	3	9, 19
Dyspnoea	DY	1	3	8
Insomnia	SL	1	3	11
Appetite loss	AP	1	3	13
Constipation	CO	1	3	16
Diarrhoea	DI	1	3	17
Financial difficulties	FI	1	3	28

* Item range is the difference between the possible maximum and the minimum response to individual items; most items take values from 1 to 4, giving range = 3.

† (revised) scales are those that have been changed since version 1.0, and their short names are indicated in this manual by a suffix “2” – for example, PF2.

For all scales, the RawScore (RS) is the mean of the component items:

$$RS = (I_1 + I_2 + \dots + I_n)/n$$

A linear transformation to 0-100 is then applied to obtain the score S:

Functional scales:

$$S = \{1 - \frac{(RS - 1)}{4}\} \times 100$$

Range

Symptom scales / items and global health status / quality of life (QoL):

$$S = \frac{RS - 1}{Range} \times 100$$

Range is the difference between the maximum possible value of RS and the minimum possible value. The QLQ-C30 has been designed so that all items in any scale take the same range of values. Therefore, the range of RS equals the range of the item values. Most items are scored 1 to 4, giving range = 3. The exceptions are the items contributing to the global health status / QoL, which are 7-point questions with range = 6.

The scales will be computed only if at least half of the required responses are non-missing. For example, role functioning (RF) and cognitive functioning (CF) each contain 2 items, and so these scales can be estimated whenever one of their constituent items is present; physical functioning contains 5 items, and so at least 3 need to have been completed. None of the single-item measures will be calculated if the question has not been answered.

6.4.2 *Description of Safety Variables*

6.4.2.1 *Adverse Events*

Adverse events (AEs) will be assessed and recorded at all study visits throughout the study from informed consent signing through EOS visit (30 days following cessation of investigational product). AEs are described in detail in Section 8.1 of the protocol.

Treatment-emergent adverse events (TEAEs) are defined as those AEs with onset during or after the first infusion of investigational product until 30 days after the last infusion of investigational product or existing events that worsened after the first infusion during the study until 30 days after the last infusion of investigational product.

Events reported with a partial onset date (eg, month and year are reported but the day is missing) will be considered treatment-emergent if it cannot be confirmed that the event onset was prior to the first dose of investigational product based on the available date entries.

Verbatim terms on case report forms will be mapped to preferred terms and system organ classes using the Medical Dictionary for Regulatory Activities (MedDRA, version 23.0).

Severity of the TEAEs will be graded based on NCI Common Terminology Criteria for

Adverse Events (CTCAE), version 5.0 (Nov 2017). Grades will be presented as mild (Grade 1), moderate (Grade 2), severe or medically significant (Grade 3), life-threatening (Grade 4) or death (Grade 5).

Adverse events of special interest (AESI) include hepatic function abnormalities (hepatotoxicity), colitis, infusion reactions (including anaphylaxis), Keratoacanthoma and potential drug-induced liver injury (DILI).

